Children's Hospital
and Health System™

**INSTITUTIONAL REVIEW BOARD
SUMMARY**

Customized Orthosis for Children with Clubfoot Following Ponseti Casting

NCT03853811

January 17, 2019

PRINCIPAL INVESTIGATOR: [name]

STUDY TITLE: Customized Orthosis for Children with Clubfoot Following Ponseti Casting

A. PURPOSE OF THE STUDY

The purpose of this study will be to design a novel customized Ankle Foot Orthosis (AFO) using 3D topographic scanner and CAD/CAM based technology then:

1. Determine differences of the patient compliance by recording the time in the brace and comparing between customized AFO and traditional straight-last shoes
2. Compare changes of foot and ankle alignments between customized AFO and traditional Mitchell shoes
3. Evaluate changes of functional outcomes between the two groups in a follow-up

B. HYPOTHESIS / SPECIFIC AIMS

We hypothesize that following Ponseti casting, the implementation of customized ankle foot orthotics (AFO) with Ponseti bracing will improve patient compliance and functional outcomes as well as lead to fewer relapses in comparison to the standard bracing with Mitchell shoes.

C. BACKGROUND, SIGNIFICANCE, AND RATIONALE

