
D. DESIGN AND METHODS

Patients will be recruited by [name] during normal clinic hours by asking existing patients if they would be willing to participate in our small study attempting to improve aspects of the bracing process. . . Patients will be randomized as they are recruited via coin flip until we have 5 spots filled in one group then assign all others to ensure 5 patients with the FO + Mitchell shoes and 5 patients with just the Mitchell shoes. Customized orthotic group will receive a customized AFOs inserted into Mitchell shoes; "Mitchell" groups will receive standard Mitchell shoes only. Inclusion criteria are as follows: less than 12 months old (no age minimum), no neuromuscular disease involved, treated by Ponseti casting, idiopathic bilateral or unilateral clubfoot, no other congenital foot deformity, and no previous open surgeries to treat the deformity. Exclusion characteristics for this study include: patients with prior surgical treatment, not treated by Ponseti casting, an underlying syndrome, or neurological disorder.

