The infant's feet will be scanned following removal of the second to last cast (allowing for orthotic production time and no extra visits) -from the middle of the tibia to the entire foot using Milwaukee Topographic system (located in the CHW Musculoskeletal Functional Assessment Center), which consists of handheld wand with two CCD cameras and one sensor to define trunk position in 3D space (Polhemus FastSCAN Scorpion, Colchester, VT). Only subjects receiving the custom orthotic insert will undergo scanning. The scanning procedure will take place after the final cast is removed and should take no longer than 5 minutes. The child will be placed into a supine position and the foot/feet will be passively manipulated to 60-70 degrees abduction and 10-15 degrees of dorsiflexion. The physician will hold the foot in place and a tech will scan the foot. Its geometry will be imported into the CAD software (Rodin4D, Paris, France) for designing the FO21. The scan will be uploaded to the epic system and a report will be generated. The report will then be sent to the Engineering team at the Orthotic Design Company, which is within the Milwaukee School of Engineering (MSOE), for manufacturing. The report will only contain raw topographic data and no identifying information. Patients will be assigned numbers to keep track of braces. The brace will be composed of biocompatible polyurethane (Elasto-75D). Following this the braces will be sent back and the patient will return to have the orthotic fitted by an orthoptist. This will likely take about a week and in the meantime all patients will wear the Mitchell shoes (Figure 1). A wireless temperature data logger (Orthotimer®) will be used to monitor brace wear for each patient (n = 10 sensors). The sensors featured a 3V battery and a data storage capacity allowing for the storage of temperature (precision of $\pm 0.1^{\circ}\text{C}$), date, and time every 15 minutes for 100 days. Batteries will not need to be changed since the minimum lifespan of the battery is 18 months. The sensors will be imbedded in the outside of the brace sandals, just above the heel, to avoid locations prone to skin irritation²². The sensor will be fused into the back of the Mitchell shoe and covered with a fabric flap that is sewn onto the shoe. The sensor and battery will not be removable and will not therefore pose a choking risk. Sensors will be calibrated upon fitting of the brace. The use of FO may cause skin redness, blisters, or rubbing. If these issues will be discovered during the regularly scheduled clinic visits, physicians will immediately request the orthotist to trim the orthosis or place additional foam on it. It must be addressed at the same time as the regularly scheduled clinic visits. It should be noted that the patient and their insurance company will be responsible for the cost of the standard Mitchell shoes and Ponseti bar, but will not be responsible for the costs of the FO, batteries, or sensor. All follow up appointments will coincide with normal clinical care except for a few additional processes during these visits (Table 1). At the end of the 6th month patients will be required to return the Orthotimer sensors but will be able to keep the custom orthotics. They should not need to get new orthotics because in the first 6 months of bracing, children often use the same shoes. We may assess the orthotic and have the orthoptist adjust the fit.

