
Table 1. Table of tasks to be performed at each clinical visit from the beginning of intervention to the end of the study period. Gray colored boxes indicate the task will be performed.

Task	Last Brace Removed	2 Week Follow Up	12 Week Follow Up	24 Week Follow Up
Check Foot				
Measure Dimeglio Score				
Scan Foot (Milwaukee Topographic System)				
Initial Survey				
Follow up Survey				
Transfer Data from Sensor				
Assess Fit and Adjust Orthotics as Needed				

Analysis of clubfoot functional outcomes will be assessed using Dimeglio Scores before and after Ponseti Casting as well as after 2, 12, and 24 weeks of bracing. Dimeglio scores are often used to assess the severity of clubfoot deformities and will give us a baseline as well as a level of improvement after casting and bracing. Dimeglio scores have been shown to provide good prognostic significance ^[5]. Other clinical parameters that we will be recording are: unilateral or bilateral CTEV, any surgeries performed (ex. achilles tenotomy, anterior tibial transfer, soft tissue release), level of brace adherence as reported by sensor, number of relapses, number of Ponseti casts needed to achieve correction, passive end dorsiflexion and abduction angles, and instances of rocker bottom deformity. The sensor to detect the body temperature will be embedded inside of the AFO and data will be stored in the sensors for three months. At follow up, the data will then be transferred to and saved to the computer via Bluetooth. In addition to these parameters we will use a parental questionnaire recording the following: occurrences of skin lesions, age of treatment initiation, age at each follow up, sex of child, prior treatments, family history of CTEV, parental marital status, insurance type, highest educational level achieved by parents, yearly family income, brace adherence as reported by parents, and reported of instances of foot slipping out of brace as well as any reasons for decreased compliance. Investigators will review the survey during clinical visits and will be able to address parent's concerns at that time. We are collecting data on these socioeconomic factors in order to help identify groups that may need additional attention or interventions in order to help reduce disparities in outcomes. Images of the child's feet in the orthotic or bracing device may be taken.

E. TOTAL NUMBER OF HUMAN RESEARCH PARTICIPANTS PROPOSED FOR THIS STUDY AT THIS SITE AND GLOBALLY. WHAT ARE THESE NUMBERS BASED ON?

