The current research and orthotic implementation may decrease the risk of clubfoot relapse and it may provide a greater level of comfort for the child throughout the bracing process. It may also allow for the use of traditional Mitchell shoes in infants with especially small and malformed feet. Specifically it may reduce the incidence of heel slippage and thus lead to a longer wear time and lower likelihood of relapse.

L. STOPPING POINTS THAT WOULD NOT ALLOW THE STUDY TO CONTINUE AS PROPOSED

Any parent who objects to their child wearing the brace will be removed from the study at their wish. If parents of the children wish to only participate in the traditional bracing protocol their wish will be respected and will not be included in either of the study cohorts.

M. IS THERE A DATA SAFETY MONITORING BOARD IN PLACE? WHO ARE IT'S MEMBERS? HOW OFTEN DO THEY MEET?

There is no safety monitoring board in place for this study.

N. DESCRIBE HOW THE CONSENT AND ASSENT PROCESS WILL TAKE PLACE. INCLUDE A LIST OF APPROPRIATELY TRAINED PERSONNEL WHO WILL BE INVOLVED.

Investigators will receive consent from all parents and answer all questions. We are requesting a waiver of assent for study because the children participants will be less than 12 months old and thus will be unable to assent.

O. PROCEDURES TO BE EMPLOYED IN ANALYZING DATA AND THE ANTICIPATED SIGNIFICANCE OF THE PROPOSED STUDY

A power analysis will be performed to determine the exact number of patients needed for future study. We will be aiming to have 10 individuals in a preliminary trial run and then move on to larger cohort studies. In children with bilateral clubfoot, each foot will be used as an independent observation in the statistical analysis. Means will be compared using Student's t-test. Statistical significance will be considered at a two-tailed level of < 0.05 .

P. FINANCIAL RELATIONSHIPS

There are no financial partnerships implicated in this study. This research is funded by the Department of Orthopaedic Surgery.

Q. ADVERTISEMENTS / FLIERS

No fliers or advertisements will be used.

R. BIBLIOGRAPHY

- ¹ Azarpira MR, Emami MJ, Vosoughi AR, Rahbari K. Factors associated with recurrence of clubfoot treated by the Ponseti method. *World J Clin Cases*. 2016;4:318.
- ² Radler BC, Manner HM, Suda R. Radiographic Evaluation of Idiopathic Clubfeet. 2007;1177-1183.
- ³ Wynne-Davies R. Family Study and The Cause of Clubfoot. *J Bone Jt Surg*. 1964;46:445-463.

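### Children are randomised, but both feet of a bilateral child enter the t-test as independent observations, which raises its false-positive rate above 5% when the two feet are positively correlated

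*Combined protocol and SAP*

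**What the plan says.** The combined protocol and SAP is a single document, and four places in it bear on this point.

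- **Randomisation (section D).** Patients are allocated by coin flip until one group is full, to "ensure 5 patients with the FO + Mitchell shoes and 5 patients with just the Mitchell shoes". The unit is the child.
- **Eligibility (section D).** The trial admits "idiopathic bilateral or unilateral clubfoot", so some children may contribute two affected feet.
- **Outcomes (sections A and D).** The second and third purposes are to "Compare changes of foot and ankle alignments between customized AFO and traditional Mitchell shoes" and to "Evaluate changes of functional outcomes between the two groups in a follow-up". Section D says: "Analysis of clubfoot functional outcomes will be assessed using Dimeglio Scores". It also lists "passive end dorsiflexion and abduction angles, and instances of rocker bottom deformity" among the recorded parameters. Brace wear, the first purpose, is logged by one sensor per patient, ten in all.
- **Analysis (section O).** "In children with bilateral clubfoot, each foot will be used as an independent observation in the statistical analysis". Means are then compared by Student's t-test at a two-tailed 0.05 level.

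No section provides a child random effect, a cluster adjustment, a mean per child or an index-foot rule.

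**The concern.** Student's t-test assumes that the observations within each arm are independent. Two feet of one child share the child, the family and the brace. Section C of the protocol itself names poor adherence to bracing as the main cause of relapse, and adherence acts on both feet together. Positive correlation is therefore plausible, although the document does not quantify it.

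If the correlation is positive, the second foot adds less information than a second child would, but the test credits it in full. The degrees of freedom rise from 8 (ten children) to as many as 18 (twenty feet), and the standard error comes out too small. A p-value below 0.05 for a foot-level measure would then overstate the evidence, and two of the three stated purposes appear to rest on such measures. Section E plans a follow-up study to test whatever this trial finds, so a spurious result could be carried forward.

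**Working it through.** **Inputs.** From the document: 5 v 5 children, unilateral and bilateral cases eligible (section D); pooled two-sample t-test on feet, two-sided 0.05 (section O). Not in the document, so varied: the number of bilateral children, and the correlation r (ICC) between the two feet of a child.

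**Step 1: reproduce the stated level.** Under the plan's own assumption (r = 0), or with no bilateral child, simulation gives 4.9 to 5.0%. The nominal 5% is right when independence holds.

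**Step 2: standard error, all children bilateral.** Each arm has 10 feet from 5 children, with foot variance σ².

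- True variance of an arm mean: σ²(1 + r)/10.
- Expected sample variance among the 10 feet: σ²[10 − (1 + r)]/9. The t-test divides this by 10.
- Ratio of true to assumed standard error: √{(1 + r) / ([10 − (1 + r)]/9)}.

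| r | Ratio | Standard error too small by |
|---|---|---|
| 0.1 | √(1.1/0.989) = 1.055 | 5% |
| 0.5 | √(1.5/0.944) = 1.260 | 21% |
| 0.9 | √(1.9/0.900) = 1.453 | 31% |

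**Step 3: exact upper bound, all bilateral and r = 1.** With n children in total, every value is duplicated, which multiplies the t statistic by √[(2n − 2)/(n − 2)]. For n = 10 this is √(18/8) = 1.500. The critical value on 18 df is 2.101, so the test rejects when the correct t on 8 df exceeds 2.101/1.500 = 1.401 in absolute value. That has probability 19.9%. Section L allows withdrawals; the same formula gives 20.4% (5 v 4), 21.0% (4 v 4) and 23.2% (3 v 3).

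**Step 4: simulation between the extremes.** Normal data, no true effect, all ten children analysed, 200,000 to 400,000 runs per cell. Type I error of the planned foot-level test:

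| Bilateral children | ICC 0.1 | ICC 0.5 | ICC 0.9 |
|---|---|---|---|
| One in total | 5.2% | 6.0% | 6.7% |
| One per arm | 5.4% | 7.1% | 9.1% |
| Two per arm | 5.6% | 8.7% | 12.5% |
| Three per arm | 5.9% | 9.9% | 15.1% |
| All ten | 6.2% | 11.7% | 18.2% |
| Each child with probability 20% | 5.4% | 6.7% | 8.6% |
| Each child with probability 50% | 5.8% | 9.1% | 13.2% |

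Independent reruns agree to within about 0.2 percentage points. At ICC 0.5 withdrawals hardly change the result: with all children bilateral, 11.7, 11.9 and 12.3% at 5 v 5, 4 v 4 and 3 v 3.

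**Step 5: where there is no inflation.** A negative correlation of −0.3 makes the test conservative: 4.1% (20% bilateral), 3.1% (50%) and 2.1% (all).

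**Step 6: check of the remedy.** A t-test on one mean per child, with 8 df at 5 v 5, gives 4.8 to 5.3% in the settings run.

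**The case against.** The strongest reply is that little hangs on this test. The trial is described as preliminary, with ten children and a follow-up study intended to confirm or refute its results. There is no stated power and no rule tying further work to p < 0.05. The first purpose, wear time, is unaffected on the natural reading. The planned power analysis is worded in individuals and patients, so it is affected only if it is built on feet. These points stand and limit the consequence. They do not remove the error, because section O sets a 0.05 test and prescribes the wrong unit for it.

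The size also depends on two quantities the document does not give. With one bilateral child or a low ICC the inflation is slight, and the 12% figure requires all ten children to be bilateral. This too is fair, and it is why ranges are shown. The direction nevertheless holds for any positive correlation once one bilateral child enrols, and a rule written for bilateral children suggests that they are expected.

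Some of the reading is inferred. No section defines the alignment measure or says outright that Dimeglio scores are recorded per foot, though section O's rule makes foot-level scoring likely. The simulations assume normal data and do not test a bounded score.

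**Conclusion.** The point holds. Section O's rule conflicts with the unit of randomisation, and nothing else in the document corrects it. For foot-level outcomes the nominal 5% test has a true rate of about 6 to 12% at ICC 0.5, depending on how many children are bilateral. Across ICC 0.1 to 0.9 the rate is about 5 to 18%, with a limit of 19.9% if all ten children are bilateral and their feet are perfectly correlated.

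Two conditions are necessary: at least one bilateral child, and positive correlation between feet. Wear time would be affected only if each child's single sensor value were entered once per foot. The rule should be corrected before any data are analysed: it is wrong as written, it bears on two of the three purposes, and the correction needs only wording.

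**What to change.** Replace the sentence in section O with wording such as:

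> The child is the unit of analysis. Wear time and other child-level measures are analysed once per child. For continuous measures taken on the foot (Dimeglio score, dorsiflexion and abduction angles), the mean of the two feet is used in bilateral children.

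A model with a child random effect and small-sample degrees of freedom is a possible alternative, but it was not tested here, and ten children give little information on the between-child variance. The mean per child is the safer choice. Whichever is used should be fixed before the data are seen.

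Two additions would help, though the correction does not depend on them. Foot-level events (relapse, rocker-bottom deformity) can be summarised per child as any versus none. The power analysis for the follow-up study should be stated to count children and use the child-level standard deviation.

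The cost is a few sentences, with no new data or visits. The test has 8 degrees of freedom instead of up to 18, so results will look less precise. When the feet are positively correlated, part of the precision given up was not real.

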We will be aiming to have 10 individuals in our preliminary trial before we move on to trying this method with larger cohorts. These numbers will allow us to run a power analysis to determine the number of individuals needed for a follow up study to confirm or refute any results we have found.

F. DRUGS OR PROCEDURES (may attach activity table if available - lab draws, EKG, chest x-rah, surgery, genetics, survey)

The participants will be scanned from the tibia to the tip of the toes by the Milwaukee Topographic system which consists of a handheld wand and sensors as well as spinal metrics. There will be a parental survey as a part of the research design. Manipulation of the foot via a trained individual will occur in order to assess the functionality and degree of deformity of the infant foot as we cannot assess gait at this early stage.

G. RISK CATEGORY:

X (1) [**45 CFR 46.404**](#) - Research not involving greater than minimal risk to the children.

(2) [**45 CFR 46.405**](#) - Research involving greater than minimal risk but presenting the prospect of direct benefit to the individual child subjects involved in the research.

(3) [**45 CFR 46.406**](#) - Research involving greater than minimal risk and no prospect of direct benefit to the individual child subjects involved in the research, but likely to yield generalizable knowledge about the subject's disorder or condition.

(4) [**45 CFR 46.407**](#) - Research that the IRB believes does not meet the conditions of 45 CFR 46.404, 46.405, or 46.406, but finds that the research presents a reasonable opportunity to further the understanding, prevention, or alleviation of a serious problem affecting the health or welfare of children.

H. RISKS AND THE PRECAUTIONS WHICH WILL BE TAKEN TO MINIMIZE RISK EXPOSURE

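### Section O compares Dimeglio means by t-test without fixing the quantity compared or using the pre-bracing score; adjusting for that score is a cheap improvement in a 5 v 5 trial

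*Combined protocol and SAP*

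**What the plan says.** The whole comparative analysis is in section O: "Means will be compared using Student's t-test", with "Statistical significance will be considered at a two-tailed level of < 0.05". No covariate, regression model or stratification appears anywhere in the document.

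Section D, after Table 1, schedules "Dimeglio Scores before and after Ponseti Casting as well as after 2, 12, and 24 weeks of bracing". It adds that these scores "will give us a baseline as well as a level of improvement after casting and bracing". A score taken after correction and before bracing is therefore planned for every child. The third purpose in section A is "Evaluate changes of functional outcomes between the two groups in a follow-up". None of these statements says whether the t-test is run on final scores or on changes, or from which of the two early scores a change would be counted.

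On size and allocation, section E says "We will be aiming to have 10 individuals in our preliminary trial before we move on to trying this method with larger cohorts". Section D says "Patients will be randomized as they are recruited via coin flip until we have 5 spots filled in one group", with the remaining children assigned so as to "ensure 5 patients with the FO + Mitchell shoes and 5 patients with just the Mitchell shoes".

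**The concern.** The quantity being tested is open. A t-test of means could use the final score, the change from before casting or the change from after casting, at any of three visits. These choices respond differently to a chance difference between arms at baseline, and an unstratified 5 v 5 allocation makes a sizeable difference likely. If one arm starts with stiffer feet, an unadjusted comparison credits part of that difference to the orthosis, or charges it to the orthosis. The score that would correct for this is already collected and is not used. The trial is also meant to inform the size of a larger study. A plain t-test gives no estimate of the baseline to follow-up correlation, which that calculation would need if the larger study adjusts for baseline.

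**Working it through.** The plan has no calculation to reproduce: the 10 children are a preliminary number, with no effect size, SD or power attached.

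**Inputs.** From the documents: 5 children per arm (section D), two-sided 0.05 and a t-test (section O), Dimeglio after casting and at 2, 12 and 24 weeks (section D). Assumed: the correlation rho between the post-casting and follow-up scores, taken from 0 to 0.7 because the documents give none; bivariate normal scores with equal SDs; the child as unit. Results are in SD units.

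**1. Chance imbalance.** The SD of the difference in baseline means is sqrt(1/5 + 1/5) = sqrt(0.4) = 0.632.
- P(difference > 0.5 SD) = 2 × [1 − Φ(0.5/0.632)] = 0.429.
- P(difference > 1 SD) = 2 × [1 − Φ(1/0.632)] = 0.114.

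**2. What an imbalance D does to the estimate.** Final scores: off by rho × D. Change from the post-casting score: off by −(1 − rho) × D. Analysis of covariance (ANCOVA): 0. For D = 1 SD and no true effect (simulation agrees with the formulas):

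| rho | Final score | Change score | ANCOVA |
|---|---|---|---|
| 0.3 | 0.30 | −0.70 | 0 |
| 0.5 | 0.50 | −0.50 | 0 |
| 0.7 | 0.70 | −0.30 | 0 |

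At that imbalance the final-score t-test rejects a true null in 6.2%, 8.3% and 10.6% of trials at rho 0.3, 0.5 and 0.7; ANCOVA stays at about 5%. At D = 0.5 SD the same t-test rejects in fewer than 5% (4.7%, 4.1%, 3.2%). Averaged over all allocations it rejects in 5%.

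**3. Precision.** Expected ANCOVA variance relative to the final-score t-test is (1 − rho²) × (1 + 1/(N − 4)), with N = 10. That is 1.17 at rho 0, 1.06 at 0.3, 0.875 at 0.5 and 0.595 at 0.7. The error degrees of freedom fall from 8 to 7, so the t multiplier rises from 2.306 to 2.365. Change-score variance relative to the same t-test is 2(1 − rho), which is better only above rho 0.5.

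Mean 95% interval width relative to the final-score t-test, from 200,000 simulated trials per correlation:

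| rho | ANCOVA, all trials | Change score, all trials | ANCOVA, trials with imbalance > 1 SD |
|---|---|---|---|
| 0 | 1.10 | 1.41 | 1.32 |
| 0.3 | 1.05 | 1.18 | 1.25 |
| 0.5 | 0.95 | 1.00 | 1.14 |
| 0.7 | 0.78 | 0.77 | 0.94 |

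Break-even for ANCOVA is at rho of about 0.41 by simulated mean width. The variance formula with the t multipliers gives 0.43.

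**The case against.** The strongest objection is that nothing here is an error. A t-test after randomisation is unbiased, with 5% type I error over allocations. That stands: the bias above is conditional on the imbalance that occurs, and a reader who infers that the planned test is invalid goes further than the documents allow.

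A reader might also infer that the trial will test change from the pre-casting score, and so mix the effect of casting into the effect of the orthosis. No section plans that test. The sentence about baseline and improvement describes what the scores are for. What is documented is only that the compared quantity and its baseline are unspecified.

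Nor is the cost of adjustment capped at 10%. That figure is an average at rho 0. In the 11% of trials with imbalance above 1 SD, the interval is 32%, 25% and 14% wider at rho 0, 0.3 and 0.5. This is the price of removing the conditional bias in just those trials.

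The unknown correlation is a fair point too. Section C cites correction in 92-100% of cases at best. If most feet are well corrected when casting ends, post-casting scores may cluster, rho may be low and the normal model may fit poorly. Section D's remark that the score is prognostic does not say which measurement is meant.

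Finally, this is a 10-child preliminary run. The 5 v 5 t-test has 29% power at a 1-SD effect and 55% at 1.5 SD, and adjustment will not make it confirmatory. The brace-time aim gains nothing, since wear time has no pre-brace value. These points limit the weight of the recommendation but do not reverse it.

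**Conclusion.** The point holds as a cheap improvement, not as a fault that invalidates the plan. Section O leaves the Dimeglio comparison undefined and makes no use of a pre-bracing score that the trial already plans to collect. The protection against chance imbalance holds at every correlation, given a linear relation with a common slope in the two arms. The gain in precision does not: it appears on average only above a correlation of about 0.4. The figures rest on normal scores, the child as unit and an assumed correlation range.

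**What to change.** In section O, state that Dimeglio at 24 weeks, and likewise at 2 and 12 weeks, will be compared between arms by linear regression on arm, with the post-casting, pre-bracing score as the single prespecified covariate, and that the estimate will be reported with its 95% interval. Use one value per child: in bilateral cases, the mean of the affected feet at both baseline and follow-up. For this outcome that replaces section O's rule of counting each foot as an independent observation, so the text should say so. Name the post-casting score as the baseline and treat the pre-casting score as descriptive.

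Where possible, record the post-casting score before the arm is revealed. Section D places the scan, done in the orthotic arm only, after the second-to-last cast in one sentence and after the final cast in another. On the first reading, allocation is known before the covariate is scored, and no blinded assessor is described. The two sentences need to be reconciled.

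The cost is a few sentences of text, no new measurements, one degree of freedom, and a wider interval if the correlation proves low.
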